3.3. Other Endpoints

- SARS-CoV-2 VOC-neutralizing titer for VOCs not already specified, by study intervention group with a BNT162b2 dose.
- SARS-CoV-2 VOC-neutralizing titer fold rise for VOCs not already specified, by study intervention group with a BNT162b2 dose.
- Presence of seroresponse for VOCs not already specified, by study intervention group with a BNT162b2 dose.

3.4. Baseline Variables

Measurements or samples collected prior to vaccination are considered the baseline data for the assessments.

3.4.1. Demographics and Medical History

The demographic variables are age at vaccination (in years), sex (male or female), race (Black/African American, American Indian, or Alaskan native, Asian, Native Hawaiian or other Pacific Islander, White, not reported), ethnicity (Hispanic/Latino/of Spanish origin, non-Hispanic/non-Latino, not reported), and racial designation (Japanese, other). In cases where more than 1 category is selected for race, the participant would be counted under the category "multiracial" for analysis. BMI will also be included in the demographic variables.

Age at the time of vaccination (in years) will be derived based on the participant's birthday. For example, if the vaccination day is 1 day before the participant's 19th birthday, the participant is 18 years old. For participants who were randomized but not vaccinated, the randomization date will be used in place of the date of vaccination for the age calculation. If the randomization date is also missing, then the informed consent date will be used for the age calculation.

Medical history will be categorized according to MedDRA.

3.4.2. E-Diary Completion

An e-diary will be considered transmitted if any data for the 3 local reactions (redness, swelling, and pain at the injection site), 7 systemic events (vomiting, diarrhea, headache, fatigue, chills, new or worsening muscle pain, and new or worsening joint pain) and fever, or use of antipyretic/pain medication to treat symptoms are present on any day. If all data are missing for all items on the e-diary for all 7 days after vaccination, then the e-diary will be considered not transmitted.

An e-diary will be considered completed if all expected data for all 7 days are available (ie, not missing). Otherwise, the e-diary will be considered incomplete. For any given day, an e-diary will be considered complete if all expected data are available.

For transmitted e-diaries, the following variables will be defined: "Day 1," "Day 2," "Day 3," "Day 4," "Day 5," "Day 6," and "Day 7".

For completed e-diaries, the following variables will be defined: "Day 1," "Day 2," "Day 3," "Day 4," "Day 5," "Day 6," "Day 7," and "Day 1 through Day 7".

"Day 1 through Day 7" is the variable for participants who completed e-diaries on all 7 days.

For e-diaries that are incomplete, an indicator variable for the percentage of days without data will be derived as follows:

- = 1, if data have been transmitted and are complete for 7 days (100%)
- = 2, if data have been transmitted and are complete for 6 days (≥75% to <100%)
- = 3, if data have been transmitted and are complete for 4 or 5 days (≥50% to <75%)
- = 4, if data have been transmitted and are complete for 2 or 3 days (≥25% to <50%)
- = 5, if data have been transmitted and are complete for 0 or 1 day $(\geq 0\%$ to <25%)

3.4.3. Prior/Concomitant Vaccines and Concomitant Medications

The name and date of administration for any concomitant medications and nonstudy vaccinations received from 28 days prior to study enrollment until the last visit (Visit 6) will be collected and recorded in the CRF.

The following concomitant medications and vaccinations will be recorded in the CRF:

- Prior receipt of any COVID-19 vaccine.
- Prior receipt of any pneumococcal vaccine.
- Licensed influenza vaccine, if received during the prior calendar year.
- Any vaccinations received from 28 days prior to study enrollment until the last visit (Visit 6).
- Prohibited medications listed in Section 10.9.6.7.1 of the protocol, if taken, will be recorded and include start and stop dates, name of the medication, dose, unit, route, and frequency.

Nonstudy vaccines and concomitant medications will be coded using the WHODD.

3.5. Safety Endpoints

Local reaction, systemic event, AE, and SAE assessments and assessments of ECG abnormalities and abnormal troponin I laboratory values are described above in the primary safety endpoints.

3.5.1. Adverse Events

As this is a Phase 1 study, with limited sample size included in each study intervention group, the value of applying the 3-tier approach is limited. Therefore, safety assessment may be best carried out using descriptive statistics only.

3.5.2. Physical Examinations, Including Vital Signs

A physical examination will be performed at the screening visit and, if clinically indicated, prior to the participant's first vaccination.

Physical examination findings collected during the study will be considered source data and will not be required to be reported. Any untoward physical examination findings that are identified during the active collection period and meet the definition of an AE or SAE will be recorded in the CRF.

The participant's oral temperature, pulse rate, and seated blood pressure will be measured at screening, prior to vaccination at Visit 1, at Visit 2, and at Visit 3. Weight and height will also be measured at screening. Any untoward vital sign findings that are identified during the active collection period and meet the definition of an AE or SAE will be recorded in the CRF.

3.5.3. Laboratory Data

The clinical safety laboratory assessments (troponin I) are described above in the primary safety endpoints.

4. ANALYSIS SETS (POPULATIONS FOR ANALYSIS)

Data for all participants will be assessed to determine if participants meet the criteria for inclusion in each analysis population prior to unblinding and releasing the database, and classifications will be documented per standard operating procedures.

Population	Description
Screened	All participants who sign the ICD.
Randomized	All participants who are assigned a randomization number in
	the IWR system.
Evaluable immunogenicity	All participants who are eligible, receive the study
	intervention to which they were randomized, have blood
	drawn for assay testing within the specified time frame
	(26-35 days after vaccination), have at least 1 valid and
	determinate assay result at the 4-week postvaccination visit,
	and have no major protocol violations.

Population	Description
mITT	All randomized participants who receive the study
	intervention and have at least 1 valid and determinate assay
	result after vaccination.
Safety	All participants who receive the study intervention.

Major protocol deviations will be determined by clinical review. A major protocol deviation is a protocol deviation that, in the opinion of the sponsor's study medical monitor, would materially affect assessment of immunogenicity or efficacy, eg, participant receipt of a prohibited vaccine or medication/treatment that might affect immune response or a medication error with suspected decrease in potency of the vaccine. The sponsor's medical monitor will identify those participants with protocol deviations before any analysis is carried out.

The APE field will be included in the PIPD form from the CORD system and is used to help identify protocol deviations that may exclude participants from a particular population. For each reporting event, the most current endorsed version of the PIPD list must be used to generate the protocol deviation data set for analysis and reporting.

The APE flags for this study are as follows:

YES-POP1 (participants excluded from the safety population)
YES-POP2 (participants excluded from the evaluable immunogenicity population)
YES-POP4 (participants identified as having multiple enrollments at different sites)

The safety analyses are based on the safety population. Participants will be summarized by study intervention group according to the study interventions they actually received. Completely missing reactogenicity e-diary data will not be imputed; missing AE dates will be handled according to the Pfizer safety rules.

For all the immunogenicity endpoints, the analysis will be based on the evaluable immunogenicity population.

An additional analysis may be performed based on the mITT population if there is a large enough difference (>10%) in sample size between the mITT population and the evaluable immunogenicity population. Participants will be summarized according to the study intervention group to which they were randomized.

Vaccinated but not randomized: These participants will be included in the safety population for safety analysis and will be reported under the study intervention based on the vaccine received but will be excluded from immunogenicity analyses.

Randomized but not vaccinated: These participants will be included in the randomized population but will be excluded from safety analyses.

Randomized but received incorrect vaccine: These participants will be excluded from the evaluable population for immunogenicity but will be included in the mITT population for immunogenicity analyses if data are available and will be reported under the study intervention based on the randomized vaccine. These participants will also be included in the safety population for safety analysis and will be reported under the study intervention based on the vaccine received.

For participants enrolling at multiple sites: Any participants enrolling at more than 1 site in the study will be removed from all populations. These participants will be followed for safety and reported separately from the other participants.

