10.11.6.7.1. Prohibited During the Study for Substudy A

Receipt of the following vaccines and medications during the time periods listed below may exclude a participant from the per-protocol analysis from that point onward; however, it is anticipated that the participant would not be withdrawn from the study (see Section 7). Medications should not be withheld if required for a participant's medical care.

- Unless considered medically necessary, no vaccines other than study intervention should be administered within 28 days before and 28 days after study vaccination at Visit 1.
- Receipt of any other (nonstudy) coronavirus vaccine from enrollment through Visit 5 (8-week follow-up visit) is prohibited.
- Receipt of any other (nonstudy) seasonal influenza vaccine from enrollment through Visit 5 (8-week follow-up visit) is prohibited.
- Receipt of chronic systemic treatment with known immunosuppressant medications, or radiotherapy, within 60 days before enrollment through conclusion of the study is prohibited.
- Receipt of systemic corticosteroids (≥20 mg/day of prednisone or equivalent) for ≥14 days is prohibited from 28 days prior to enrollment through 28 days after administration of the study intervention.
- Receipt of blood/plasma products, immunoglobulins, or monoclonal antibodies, from 60 days before study intervention administration through conclusion of the study.

 Prophylactic antipyretics and other pain medication to prevent symptoms associated with study intervention administration are not permitted. However, if a participant is taking a medication for another condition, even if it may have antipyretic or pain-relieving properties, it should not be withheld prior to study vaccination.

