10.11.9.2. Analysis Sets for Substudy A

For purposes of analysis, the following analysis sets are defined in Substudy A:

Population	Description
Screened	All participants who sign the ICD.
Randomly assigned to	All participants who are assigned a randomization number in
study intervention	the IWR system regardless of whether or not the study
	intervention was administered.
Evaluable immunogenicity	All participants who are eligible, receive the study
	intervention to which they were randomized, have blood
	drawn for assay testing within the specified time frame after
	vaccination, have at least 1 valid and determinate assay result
	at the 4-week postvaccination visit, and have no major
	protocol violations.
mITT immunogenicity	All randomized participants who receive the study
	intervention and have at least 1 valid and determinate assay
	result after vaccination.
Safety	All participants who receive the study intervention.

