10.12.9.1.1. Estimands for Substudy B

10.12.9.1.1.1. Primary Estimands/Coprimary Estimands for Substudy B

The estimands to evaluate the safety objective are based on the safety population. These estimands estimate vaccine safety after study intervention. Completely missing e-diary data will not be imputed; missing AE dates and missing AE intensity will be handled according to Pfizer safety rules. Missing e-diary data not recorded in the e-diary will be recorded on the AE CRF. Therefore, the primary analysis will use reactogenicity recorded as AEs in the CRF to impute the missing e-diary data.

10.12.9.1.1.2. Secondary Estimands for Substudy B

The secondary estimands corresponding to each secondary objective are described in the table in Section 10.12.3.

The estimands to evaluate the immunogenicity objectives are based on the evaluable immunogenicity population. These estimands estimate the immune response after study intervention administration in the hypothetical setting where participants follow the study schedules and protocol requirements as directed. Missing immunogenicity results will not be imputed, as MCAR is assumed. For participants who discontinue from the study or have major protocol violations, all postdiscontinuation or postviolation observations will be censored.

Immunogenicity results that are below the LLOQ will be set to $0.5 \times LLOQ$ in the analyses.

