 - Undergoing blood collection outside of the defined window (26 to 35 days, inclusive, after vaccination).

All data after intercurrent events, if collected, will be excluded.

- Population-level summary:
 - HAI GMTs at each time point and GMFRs from before vaccination to each time point after vaccination, and the proportion of participants achieving HAI seroconversion at each time point and the proportion of participants with HAI titers ≥1:40 before vaccination and at each time point after vaccination, will be estimated for each strain, by study intervention group with qIRV, for participants 18 through 64 years of age and ≥65 years of age separately.
 - SARS-CoV-2 GMT at each time point and GMFRs from before vaccination to each time point after vaccination, and the proportion of participants with seroresponse at 1, 4, and 8 weeks after vaccination, will be estimated for each strain by study intervention group with a BNT162b2 dose, for participants 18 through 64 years of age and ≥65 years of age separately.

*Original refers to the ancestral strain (Wuhan-Hu-1; USA-WA1/2020), also referred to in the protocol as the reference strain.

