6.2. Secondary Endpoints

6.2.1. Immunogenicity Endpoints

6.2.1.1. Main Analysis

- Estimand strategy: Hypothetical approach (Section 2.2.2).
- Analysis set: Evaluable immunogenicity population (Section 4).
- Analysis methodology: Descriptive summary statistics (Section 5.2.2).
- Analysis timing: 1, 4, and 8 Weeks after study intervention administration.
- Intercurrent events and missing data: All data collected after or at intercurrent events will be excluded. Antibody titers below the LLOQ will be treated as specified in Section 5.3.2. Missing data will not be imputed.
- Reporting results:
 - The SARS-CoV-2 GMT at each time point and GMFRs from before vaccination to
 each time point after vaccination, and the proportion of participants with seroresponse
 at 1, 4, and 8 weeks after vaccination, will be estimated for each strain, by study
 intervention group with a BNT162b2 dose, and separately by age group.
 - Descriptive statistics, including the sample size (n), GMTs, GMFRs, and 95% CI for the GMTs and GMFRs, will be presented for each strain by study intervention group with qIRV (Section 5.2.2), for participants 18 through 64 years of age and ≥65 years of age separately.
 - The proportion of participants achieving HAI seroconversion and the associated 2-sided Clopper-Pearson 95% CIs will be provided for each strain by study intervention group with qIRV, for participants 18 through 64 years of age and ≥65 years of age separately.
 - o The proportion of participants with HAI titers ≥1:40 before vaccination and at each time point after vaccination and the associated 2-sided Clopper-Pearson 95% CIs will be provided for each strain by study intervention group with qIRV, for participants 18 through 64 years of age and ≥65 years of age separately.
 - HAI GMTs for each strain and the associated 95% CIs will be plotted by study intervention group with qIRV, for participants 18 through 64 years of age and ≥65 years of age separately.
 - HAI seroconversion rate for each strain, along with the associated 95% CIs, will be presented by study intervention group with qIRV, for participants 18 through 64 years of age and ≥65 years of age separately.

- SARS-CoV-2 GMT at each time point and GMFRs from before vaccination to each time point after vaccination, and the proportion of participants with seroresponse at 1, 4, and 8 weeks after vaccination, will be provided for each strain by study intervention group with a BNT162b2 dose, and separately by age group.

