4. ANALYSIS SETS (POPULATIONS FOR ANALYSIS)

Data for all participants will be assessed to determine if participants meet the criteria for inclusion in each analysis population prior to unblinding and releasing the database and classifications will be documented per standard operating procedures.

Population	Description
Screened	All participants who sign the ICD.
Randomized	All participants who are assigned a randomization number in the IRT system.

Population	Description
Evaluable immunogenicity	All participants who are eligible, receive the study intervention to which they were randomized, have blood drawn for assay testing within the specified time frame after vaccination (26-35 days after vaccination), have at least 1 valid and determinate assay result at the 4-week postvaccination visit, and have no major protocol violations.
mITT immunogenicity	All randomized participants who receive the study intervention and have at least 1 valid and determinate assay result after vaccination.
Safety	All participants who receive the study intervention.

For determination of the evaluable immunogenicity population(s), the last criteria of exclusions due to major protocol violations will be determined via clinical review. The remainder of the criteria will be determined programmatically.

A major protocol violation is a protocol violation that, in the opinion of the sponsor's global medical monitor, would materially affect assessment of immunogenicity, eg, participant receipt of a prohibited vaccine, medication that might affect immune response, or a medication error with suspected decrease in potency of the vaccine. The global medical monitor from the sponsor will identify those participants with a protocol violation prior to any immunogenicity analysis in the study.

For safety, reporting will be as administered and, for immunogenicity, reporting will be as randomized.

For all the immunogenicity endpoints, the analysis will be based on the evaluable immunogenicity population.

An additional analysis may be performed based on the mITT population if there is a large enough difference (>10%) in sample size between the mITT population and the evaluable immunogenicity population.

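### In Substudy A the evaluable immunogenicity set drops a participant from every time point for a major violation at any time, whereas the estimand and main analysis drop only data from the violation onward

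*SAP*

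**What the plan says.** Two rules cover a Substudy A participant who has a major violation partway through follow-up.

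**Whole-participant rule.** The Substudy A SAP, Section 4, admits to the evaluable immunogenicity population only participants who satisfy all listed criteria "and have no major protocol violations". No date is attached. The section bases every immunogenicity endpoint on this population and flags exclusion from it with a single participant-level code. Protocol 10.11.9.2 has the same two closing conditions ("at the 4-week postvaccination visit, and have no major" protocol violations).

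**From-the-event rule.**
- Protocol 10.11.6.7.1: receiving a listed vaccine or medication "may exclude a participant from the per-protocol analysis from that point onward".
- Substudy A SAP 2.2.2, which lists major protocol deviations among the intercurrent events: "All data after intercurrent events, if collected, will be excluded".
- Substudy A SAP 6.2.1.1: "All data collected after or at intercurrent events will be excluded".

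For Substudy B, protocol 10.12.9.1.1.2 also censors by time ("all postdiscontinuation or postviolation observations will be censored"), while the Substudy B SAP, Section 4, requires participants to "have at least 1 valid and determinate assay result at the 4-week postvaccination visit, and have no major protocol violations", again with no time limit. Protocol 10.12.9.2 matches that SAP.

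**The concern.** The two rules give different data sets for the same person. If the whole participant is removed, no pre-event data remain for the from-the-event rule to keep. Section 6.2.1.1 of the Substudy A SAP names both the evaluable set and the from-the-event exclusion, so the main analysis contradicts itself.

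The week-4 titer is secondary in both documents, and whether it is analyzed can depend on what the participant does after the blood was drawn. That is selection on a post-outcome event. The result is no longer the hypothetical-strategy estimand of SAP 2.2.2, which calls for removing only what follows the event. Section 4 also requires the latest endorsed deviation list at each reporting event, so an unchanged week-4 titer could be in one report and out of the next.

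**Working it through.** **1. Trace one case through both rules.** Take a Substudy A participant in a group that receives BNT162b2, with valid samples at Visits 3, 4 and 5, who gets a nonstudy coronavirus vaccine on Day 40.

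- Timing (protocol 10.11.1): Visit 3 is 6 to 8 days after Visit 1, Visit 4 is 26 to 30 days after, and Visit 5 is 52 to 60 days after. The event falls between the week-4 and week-8 draws.
- Status: protocol 10.11.6.7.1 prohibits this vaccine through Visit 5.
- Classification: Section 4 of the SAP gives receipt of a prohibited vaccine that might affect the immune response as an example of a major deviation. Week 8 is analyzed (6.2.1.1) and its neutralizing titer would plausibly be affected, so the medical monitor could reasonably class the event as major.

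| Titer | From-the-event rule (SAP 2.2.2, 6.2.1.1; protocol 10.11.6.7.1) | Evaluable set (SAP Section 4; protocol 10.11.9.2) |
|---|---|---|
| Week 1 | kept | removed |
| Week 4 | kept | removed |
| Week 8 | removed | removed |

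The rules disagree on two of three time points, including the secondary one.

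**2. The plan's own figures.** Protocol 10.11.9.5 plans about 30 participants per group and stratum: 6 groups × 2 strata × 30 = 360, as stated. Table 7 is 1 − (1 − p)^30. At p = 0.5%, 1%, 2%, 5% and 7% this gives 13.96%, 26.03%, 45.45%, 78.54% and 88.66%, matching the printed 14.0%, 26.0%, 45.5%, 78.5% and 88.7%. Neither figure is in question; they fix n = 30.

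**3. Illustrative precision cost.** Neither document gives a violation rate, so the number lost is an assumption. GMT intervals use the Student t distribution on log titers (SAP 5.2.2.1), so the half-width in SD units is h(n) = t(0.975, n − 1)/√n.

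| Lost of 30 (assumed) | n | Share lost | h(n) | Change from n = 30 |
|---|---|---|---|---|
| 0 | 30 | 0% | 0.3734 | – |
| 1 | 29 | 3.3% | 0.3804 | +1.9% |
| 2 | 28 | 6.7% | 0.3878 | +3.8% |
| 3 | 27 | 10.0% | 0.3956 | +5.9% |
| 6 | 24 | 20.0% | 0.4223 | +13.1% |

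**4. Would the mITT analysis catch it?** Section 4 says an mITT analysis may be done if the two sets differ in size by more than 10%, without saying whether per group or overall. If per group, 3/30 = 10.0% does not exceed the threshold and 4/30 = 13.3% does. SAP 6.2.1.2 offers an mITT summary without that threshold, but also as optional. It uses the treatment-policy strategy, so it would retain the post-violation week-8 titer as well. It does not restore the stated estimand.

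**The case against.** The case on the other side limits the point in several ways.

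- **A reader might infer that the SAP departs from the protocol.** It does not. Protocol 10.11.9.2 and 10.12.9.2 carry the same criteria as the SAPs, so the inconsistency runs through both documents and both need editing.
- **A reader might infer that requiring a week-4 result is part of the error**, because an early dropout or someone who misses Visit 4 loses other titers. The documents do not support that. The requirement ("determinate assay result at the 4-week postvaccination visit") is an openly stated design choice. Protocol 10.11.6.7.1 concerns prohibited vaccines and medications, and the intercurrent events in SAP 2.2.2 include neither discontinuation nor a missed visit. No stated Substudy A rule is broken.
- **A reader might infer a large reach-back in Substudy B**, where nonstudy coronavirus and influenza vaccines are prohibited throughout the study but the only postvaccination draw is at week 4. The Substudy B SAP counts a violation as major only if it would materially affect the immunogenicity assessment. A vaccine given months after the sole draw cannot affect that titer, so the definition screens out most such events. Only a wording mismatch remains.
- **A reader might infer a directional bias**, for example that qIRV-only participants would more often seek a COVID-19 vaccine. The documents give no uptake data, and those groups have no SARS-CoV-2 titer endpoint in the Substudy A SAP.

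It is also fair that protocol 10.11.6.7.1 says may, and that the medical monitor decides what is major. In Substudy A this does not dispose of the point. A Day-40 vaccine can properly be called major because of week 8, and the set definition then removes weeks 1 and 4 as well.

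**Conclusion.** The inconsistency stands, confined mainly to Substudy A and to major violations that follow a valid draw. The undated criterion in the evaluable set defeats the from-the-event rule in the estimand and main analysis, and makes the week-4 secondary analysis depend on later events. Weeks 1 and 8 matter less under Amendment 6, which makes them exploratory; the Substudy A SAP, written against Amendment 2, still lists them as secondary.

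The size is unknown. The precision loss is modest under the assumed counts (about 6% wider at 3 of 30 lost), and the direction of any selection effect cannot be stated. The conclusion rests on comparing the texts and on the assumption that some events between weeks 4 and 8 are classed as major.

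**What to change.** In Section 4 of the Substudy A SAP, and identically in protocol 10.11.9.2, replace the undated criterion with one applied per time point: *no major protocol violation on or before that sample*. Leave the week-4-result requirement as it is. Events preceding every postvaccination sample, such as ineligibility or receiving the wrong vaccine, still remove the participant throughout, so only valid earlier titers are restored.

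Add the same time limit to the Substudy B SAP, Section 4, and protocol 10.12.9.2 so that they agree with protocol 10.12.9.1.1.2. Little should change there in practice.

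The cost is one phrase in each of four definitions and a comparison of violation date with sample date in the population flag. The small downside is that n may differ between time points within a group, so tables should show n at each one.
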